7.5 Preparation/Handling/Storage/Accountability

The investigational product should be stored in a secure area according to local regulations. It is the responsibility of the investigator to ensure that investigational product is only dispensed to

study Participants. The investigational product must be dispensed only from official study sites by authorized personnel according to local regulations.

The product storage manager should ensure that the study treatment is stored in accordance with the environmental conditions (temperature, light, and humidity) as determined by BMS. If concerns regarding the quality or appearance of the study treatment arise, the study treatment should not be dispensed and contact BMS immediately.

Study treatment not supplied by BMS will be stored in accordance with the package insert.

Investigational product documentation (whether supplied by BMS or not) must be maintained that includes all processes required to ensure drug is accurately administered. This includes documentation of drug storage, administration and, as applicable, storage temperatures, reconstitution, and use of required processes (eg, required diluents, administration sets).

- Further guidance and information for final disposition of unused study treatment are provided in [Appendix 2](#).

7.5.1 Retained Samples for Bioavailability / Bioequivalence

Not applicable.

7.6 Treatment Compliance

Study treatment compliance will be periodically monitored by drug accountability (including review of dosing diary cards, as applicable). Drug accountability should be reviewed by the site study staff at each visit to confirm treatment compliance. Sites should discuss discrepancies with the participant at each on-treatment study visit.

[REDACTED]

[Redacted text block containing multiple paragraphs of blacked-out content]

[REDACTED]

7.8 Treatment After the End of the Study

At the conclusion of the study, participants who continue to demonstrate clinical benefit will be eligible to receive BMS supplied study treatment for the maximum treatment duration specified in protocol [Section 7.1](#). Study treatment will be provided via an extension of the study, a rollover study requiring approval by responsible health authority and ethics committee or through another mechanism at the discretion of BMS.

BMS reserves the right to terminate access to BMS supplied study treatment if any of the following occur: a) the study is terminated due to safety concerns; b) the development of the nivolumab, ipilimumab, cabozantinib, or sunitinib is terminated for other reasons, including but not limited to lack of efficacy and/or not meeting the study objectives; c) the participant can obtain medication from a government sponsored or private health program. In all cases BMS will follow local regulations.

8 DISCONTINUATION CRITERIA

8.1 Discontinuation from Study Treatment

Participants **MUST** discontinue investigational product (and non-investigational product at the discretion of the investigator) for any of the following reasons:

- Participant's request to stop study treatment. Participants who request to discontinue study treatment will remain in the study and must continue to be followed for protocol specified follow-up procedures. The only exception to this is when a participant specifically withdraws consent for any further contact with him/her or persons previously authorized by participant to provide this information
- Any clinical adverse event (AE), laboratory abnormality or intercurrent illness which, in the opinion of the investigator, indicates that continued participation in the study is not in the best interest of the participant
- Termination of the study by Bristol-Myers Squibb (BMS)
- Loss of ability to freely provide consent through imprisonment or involuntarily incarceration for treatment of either a psychiatric or physical (eg, infectious disease) illness. (Note: Under specific circumstances, and only in countries where local regulations permit, a participant who has been imprisoned may be permitted to continue as a participant. Strict conditions apply and BMS approval is required.)
- Criteria listed in 8.1.1
- Disease progression of RCC or occurrence of a secondary malignancy which requires systemic therapy for treatment

Refer to the Schedule of Activities for data to be collected at the time of treatment discontinuation and follow-up and for any further evaluations that can be completed.

In the case of pregnancy, the investigator must immediately notify the BMS Medical Monitor/designee of this event. In most cases, the study treatment will be permanently discontinued in an appropriate manner (eg, dose tapering if necessary for participant safety). Please call the BMS Medical Monitor within 24 hours of awareness of the pregnancy. If the investigator determines a possible favorable benefit/risk ratio that warrants continuation of study treatment, a discussion between the investigator and the BMS Medical Monitor/designee must occur.

All participants who discontinue study treatment should comply with protocol specified follow-up procedures as outlined in [Section 2](#). The only exception to this requirement is when a participant withdraws consent for all study procedures including post-treatment study follow-up or loses the ability to consent freely (ie, is imprisoned or involuntarily incarcerated for the treatment of either a psychiatric or physical illness).

If study treatment is discontinued prior to the participant's completion of the study, the reason for the discontinuation must be documented in the participant's medical records and entered on the appropriate case report form (CRF) page.

8.1.1 Nivolumab and Ipilimumab Dose Discontinuation (Arms A and B)

CA2099ER Global Revised Protocol 01

Implementation of CA2099ER Global Revised Protocol 01 stops further randomization into Arm B. Participants previously randomized to Arm B continue with Arm B treatment and continue with Arm B clinical planned events, per protocol.

The assessment for discontinuation of nivolumab, ipilimumab, and cabozantinib should be made separately for each study drug. Although there is overlap among the discontinuation criteria, if

discontinuation criteria are met for one study drug but not the other(s), it may be acceptable to continue treatment with the study drug(s) that are not felt to be related the toxicity, as specified below. If the investigator considers the toxicity to be related to all study drugs or is unable to determine which of the study drug(s) in Arm A or Arm B are the cause of toxicity, then all study drugs in the treatment regimen should be discontinued, and the recommendations for management of toxicity related to all study drugs should be promptly initiated.

Nivolumab and/or ipilimumab treatment should be permanently discontinued for any of the following:

- Any Grade 2 drug-related uveitis, eye pain or blurred vision that does not respond to topical therapy and does not improve to Grade 1 severity within the re-treatment period OR requires systemic treatment
- Any Grade 3 non-skin, drug-related adverse event lasting > 7 days, or recurs with the following exceptions for laboratory abnormalities, diarrhea, colitis, neurologic toxicity, drug-related uveitis, pneumonitis, bronchospasm, hypersensitivity reactions, infusion reactions, and endocrinopathies:
 - Grade 3 drug-related diarrhea, colitis, neurologic toxicity, uveitis, pneumonitis, bronchospasm, myocarditis, hypersensitivity reaction, or infusion reaction of any duration requires discontinuation. NOTE: The diagnosis of colitis should be supported by findings on colonoscopy whenever possible.
 - Grade 3 drug-related endocrinopathies, adequately controlled with only physiologic hormone replacement do not require discontinuation. Adrenal insufficiency requires discontinuation regardless of control with hormone replacement.
 - Grade 3 drug-related laboratory abnormalities do not require treatment discontinuation except:
 - ◆ Grade 3 drug-related thrombocytopenia > 7 days or associated with bleeding requires discontinuation
 - ◆ Any drug-related liver function test (LFT) abnormality that meets the following criteria require discontinuation:
 - Grade ≥ 3 drug-related AST, ALT or Total Bilirubin requires discontinuation*
 - Concurrent AST or ALT > 3 x ULN and total bilirubin > 2x ULN
- Any Grade 4 drug-related adverse event or laboratory abnormality (including but not limited to creatinine, AST, ALT, or Total Bilirubin), except for the following events which do not require discontinuation:
 - Grade 4 neutropenia ≤ 7 days
 - Grade 4 lymphopenia or leukopenia or asymptomatic amylase or lipase

- Isolated Grade 4 electrolyte imbalances/abnormalities that are not associated with clinical sequelae and are corrected with supplementation/appropriate management within 72 hours of their onset
- Grade 4 drug-related endocrinopathy adverse events, such as, hyper- or hypothyroidism, or glucose intolerance, which resolve or are adequately controlled with physiologic hormone replacement (corticosteroids, thyroid hormones) or glucose-controlling agents, respectively, may not require discontinuation after discussion with and approval from the BMS Medical Monitor or designee.
- Any event that leads to delay in dosing lasting > 6 weeks from the previous dose requires discontinuation, with the following exceptions:
 - Dosing delays to allow for prolonged steroid tapers to manage drug-related adverse events are allowed.
 - Dosing delays lasting > 6 weeks from the previous dose that occur for non-drug-related reasons may be allowed if approved by the BMS Medical Monitor or designee.

Prior to re-initiating treatment in a participant with a dosing delay lasting > 6 weeks, the BMS Medical Monitor or designee must be consulted. Tumor assessments should continue as per protocol even if dosing is delayed. Periodic study visits to assess safety and laboratory studies should also continue every 6 weeks or more frequently if clinically indicated during such dosing delays.

- Any adverse event, laboratory abnormality, or intercurrent illness which, in the judgment of the Investigator, presents a substantial clinical risk to the participant with continued nivolumab dosing.

Participants in Arm B who meet any of the discontinuation criteria above prior to Cycle 3 must discontinue both nivolumab and ipilimumab and may not receive nivolumab monotherapy maintenance.

Participants in Arm B who meet any of the discontinuation criteria above after Cycle 3 or Cycle 4 may be able to proceed to Cycle 5 (skipping Cycle 4 if needed) to begin nivolumab monotherapy maintenance if the toxicity is felt to be related mainly to ipilimumab, only after discussion with and approval by the BMS Medical Monitor or designee.

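### As worded, Protocol 8.1.1 lets controlled Grade 4 adrenal insufficiency continue on nivolumab with approval while controlled Grade 3 must stop; the Grade 4 exception should exclude it

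*Protocol*

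**What the plan says.** Protocol 8.1 lists the reasons for which a participant must come off study drug, and "Criteria listed in 8.1.1" is one of them. Section 8.1.1 then sets out the nivolumab and ipilimumab criteria as bullets, any one of which is enough.

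- **Grade 3 bullet.** Non-skin, drug-related Grade 3 events that persist beyond a week or recur lead to discontinuation, with exceptions. One exception is a sub-bullet of two consecutive sentences. The first is "Grade 3 drug-related endocrinopathies, adequately controlled with only physiologic hormone replacement do not require discontinuation". The second is "Adrenal insufficiency requires discontinuation regardless of control with hormone replacement". The second sentence states no grade.
- **Grade 4 bullet.** Any Grade 4 drug-related event leads to discontinuation, again with exceptions. One covers "Grade 4 drug-related endocrinopathy adverse events, such as, hyper- or hypothyroidism, or glucose intolerance", and continues: "which resolve or are adequately controlled with physiologic hormone replacement (corticosteroids, thyroid hormones) or glucose-controlling agents, respectively, may not require discontinuation". The relief is conditional: such events "may not require discontinuation after discussion with and approval from the BMS Medical Monitor or designee".
- **Investigator's judgment.** 8.1.1 also stops nivolumab for any event that, "in the judgment of the Investigator, presents a substantial clinical risk to the participant with continued nivolumab dosing". Section 8.1 has a similar stop based on the participant's best interest.

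Section 7.4.1.1 delays nivolumab for non-skin drug-related events of Grade 2 or more, fatigue excepted. Section 7.4.3.1 allows dosing to restart when a drug-related endocrinopathy is held by physiologic replacement alone. That resume rule has no grade limit and no adrenal exclusion.

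**The concern.** The protocol singles out adrenal insufficiency as the endocrine event for which good control on replacement does not save the participant from stopping. The Grade 4 exception grants relief for exactly that kind of control and does not repeat the exclusion. Taken literally, the more severe event has a route to continued dosing that the less severe event lacks.

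Because 8.1 makes these criteria mandatory, a site with a controlled Grade 4 case needs one answer. As drafted, one investigator could stop nivolumab on the adrenal sentence while another asks the Medical Monitor for leave to continue under the Grade 4 exception. Each could point to the text. What is at stake is consistent handling of a serious event, with a small safety component.

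**Working it through.** There is no figure to reproduce. The check is a reading of the rules side by side.

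**1. Where the adrenal sentence sits.** It is the second sentence of a sub-bullet that opens with Grade 3 endocrinopathies, under a Grade 3 parent bullet. It runs on in the same line as the first sentence, so its placement does not depend on how indentation survived text extraction.

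**2. Whether the Grade 4 exception can reach adrenal insufficiency.** Its examples are thyroid events and glucose intolerance, but they are introduced as examples. It names corticosteroids as a physiologic replacement. Exclusion criterion 1c in Protocol 6.2 refers to adrenal replacement steroids, so the protocol itself links steroid replacement to the adrenal gland. SAP 7.1.1.1 and 7.1.1.3 class adrenal disorders and adrenal insufficiency as endocrine events. Nothing in the exception takes adrenal insufficiency out.

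**3. How the section widens scope elsewhere.** Under the same Grade 3 bullet, the liver rule states its reach: "Grade ≥ 3 drug-related AST, ALT or Total Bilirubin requires discontinuation". The adrenal sentence has no such marker. This makes a Grade 3-only reading natural but does not compel it.

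**4. The two readings and the effect of the fix.** On the nested reading, the adrenal sentence is confined to its Grade 3 bullet. On the stand-alone reading, it is a specific rule that applies at every grade and overrides the general Grade 4 exception.

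| Drug-related adrenal insufficiency | Nested reading | Stand-alone reading | After the fix below |
|---|---|---|---|
| Grade 2 | Delay, then resume rule | Stop | Left as it is on either reading |
| Grade 3, controlled | Stop | Stop | Stop |
| Grade 4, controlled | May continue with approval | Stop | Stop |
| Grade 4, not resolved or controlled | Stop | Stop | Stop |

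The fix changes one row, controlled Grade 4, and only on the nested reading. It works without settling the reach of the adrenal sentence: once adrenal insufficiency is outside the exception, the Grade 4 bullet itself requires the stop.

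**5. Safeguards on the affected row.** There are three: one Medical Monitor approval and two investigator-judgment stops (8.1 and 8.1.1).

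**6. What is not known.** The documents give no frequency for the event. Section 7.4.1.1 places the management algorithms, including the endocrinopathy one, in Appendix 5, which is not in the text available.

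**The case against.** The strongest reply is that mandatory stopping at both grades is the better reading already. The lead-in makes any listed criterion sufficient, and the adrenal sentence is specific and categorical. The Grade 4 exception is general, permissive and silent on adrenal insufficiency. The word corticosteroids need not point there, since SAP 7.1.1.3 lists hypophysitis as a separate endocrine event. Few authors would intend Grade 3 to be stricter than Grade 4. All of this stands as evidence of intent. It does not supply a sentence that decides the matter, and a mandatory stopping rule should not rest on inference.

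It is also fair to say that inconsistency is contained. An investigator on the nested reading cannot continue alone; the request goes to the sponsor's Medical Monitor or designee, who can apply one interpretation. An investigator on the other reading errs on the cautious side. That limits the harm. It does not tell the Medical Monitor whether approval is available for this event.

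A further objection concerns the remedy. A reader might infer that the adrenal sentence should simply be reworded to cover drug-related events of Grade 3 or higher, on the liver rule's pattern. The documents do not support that. The sentence is ungraded, and on the stand-alone reading it also stops Grade 2. The rewording could move Grade 2 from stopping to delay and resumption, which is less protection. It would also add a drug-related condition that the sentence itself does not contain. This objection stands in full, and the fix below avoids that wording.

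**Conclusion.** The two rules conflict as worded. A controlled Grade 4 adrenal insufficiency may continue with approval, although the same event at Grade 3 must stop. The likely intent is to stop at both grades.

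The effect is confined to controlled, drug-related Grade 4 adrenal insufficiency in participants receiving nivolumab, subject to the three safeguards above. Sample size, power, alpha and the planned analyses are untouched. This is a low-priority safety-wording correction, held with medium confidence.

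Two stronger conclusions are tempting and should not be drawn. A reader might infer that the protocol deliberately reverses the order of severity; the stand-alone reading gives no reversal, so the text does not show that. A reader might also infer that the whole protocol leaves the question open. The finding covers only the visible text of 8.1.1 and 7.4.3.1, because Appendix 5 could not be checked and may address the point.

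**What to change.** 1. Leave the adrenal sentence in the Grade 3 sub-bullet of 8.1.1 unchanged.
2. In the Grade 4 endocrinopathy exception of 8.1.1, add *other than adrenal insufficiency*. The direction follows from the protocol's own statement that control on replacement does not matter for this event.
3. In the endocrinopathy resume rule of 7.4.3.1, add *except as specified in Section 8.1.1*, so that it cannot be read as overriding the stop. The same list already defers to 8.1.1 for delays beyond six weeks.
4. Do not attach a Grade 3-or-higher, drug-related qualifier to the adrenal sentence unless the sponsor first confirms that Grade 2 adrenal insufficiency was not meant to require discontinuation.
5. Check the Appendix 5 endocrinopathy algorithm against the new wording.

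The cost is a short edit to two bullets, bundled with the next amendment. Under Appendix 2, an amendment needs IRB/IEC approval and, where applicable, local health authority approval. No new data, visits or participants are required.

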8.1.2 Cabozantinib Dose Discontinuation

Permanently discontinue cabozantinib for participants with any of the following:

- Any requirement for more than 2 cabozantinib dose reductions (ie, reduction to less than 20 mg every other day)
- Any Grade \geq 2 drug-related arterial thromboembolic events, including cerebrovascular ischemia, cardiac ischemia/infarction, peripheral or visceral arterial ischemia
- Any Grade \geq 3 drug-related hemorrhage
- Grade 4 hypertension or persistent Grade 3 hypertension despite optimal medical management and cabozantinib dose reduction
- Drug-related reversible posterior leukoencephalopathy syndrome

- Development of drug-related fistula or GI perforation
- Drug-related nephrotic syndrome
- Any drug-related liver function test (LFT) abnormality that meets the following criteria requires discontinuation:
 - AST or ALT > 8 x ULN.
 - Concurrent AST or ALT > 3 x ULN and total bilirubin >2 x ULN, consistent with potential drug-induced liver injury (see [Section 9.2.7](#)).
- Any Grade 4 drug-related adverse event or laboratory abnormality, with the following exceptions:
 - Grade 4 neutropenia ≤ 7 days
 - Grade 4 lymphopenia or leukopenia
 - Grade 4 amylase or lipase abnormalities that are not associated with symptoms or clinical manifestations of pancreatitis
 - Isolated Grade 4 electrolyte abnormalities that are not associated with clinical sequelae and are corrected with supplementation/appropriate management within 72 hours of their onset
- Any dosing interruption lasting > 6 weeks unless the BMS Medical Monitor or designee is consulted and agrees with the rationale for resuming therapy after a delay > 6 weeks. Note that tumor assessments should continue as per protocol even if dosing is interrupted.
- Any adverse event, laboratory abnormality, or intercurrent illness which, in the judgment of the Investigator, presents a substantial clinical risk to the participant with continued cabozantinib dosing.

8.1.3 Sunitinib Dose Discontinuation

Treatment with sunitinib should be permanently discontinued for any of the following:

- Any requirement for more than 2 sunitinib dose reductions (ie, reduction to less than 25 mg daily)
- Any Grade drug-related arterial thrombosis.
- Grade 4 drug-related hemorrhage or recurrent Grade 3 drug-related hemorrhage after dose reduction.
- Grade 4 drug-related symptomatic venous thrombosis.
- Grade 4 drug-related cardiac toxicity.
- Grade 4 hypertension or persistent Grade 3 hypertension despite optimal medical management and sunitinib dose reduction
- Any drug-related liver function test (LFT) abnormality that meets the following criteria requires discontinuation:
 - AST or ALT > 8 x ULN.
 - Concurrent AST or ALT > 3 x ULN and total bilirubin >2 x ULN, consistent with potential drug-induced liver injury (see [Section 9.2.7](#)).
- Any other Grade 4 drug-related adverse event or laboratory abnormality, with the following exceptions:

- Grade 4 neutropenia \leq 7 days
- Grade 4 lymphopenia or leukopenia
- Grade 4 amylase or lipase abnormalities that are not associated with symptoms or clinical manifestations of pancreatitis
- Isolated Grade 4 electrolyte abnormalities that are not associated with clinical sequelae and are corrected with supplementation/appropriate management within 72 hours of their onset
- Any dosing interruption lasting $>$ 6 weeks unless the BMS Medical Monitor or designee is consulted and agrees with the rationale for resuming therapy after a delay $>$ 6 weeks. Note that tumor assessments should continue as per protocol even if dosing is interrupted.
- Any adverse event, laboratory abnormality, or intercurrent illness which, in the judgment of the Investigator, presents a substantial clinical risk to the participant with continued sunitinib dosing.

